## **Botulinum Toxin Drug Product**

Botulinum toxin under the names BOTOX, JEUVEAU, XEOMIN, and DYSPORT, is an FDA approved drug for the treatment of Moderate to severe glabellar lines, moderate to severe lateral canthal lines, known as crow's feet, strabismus, blepharospasm, neurogenic detrusor overactivity and chronic migraine.

It is a crystalline preparation of BT type A. This agent should be considered exempt from IND requirements as it meets the below IND criteria.

The research is not intended to be reported to the FDA as a well-controlled study in support of a new indication for use nor intended to be used to support any other significant change in the labeling for the drug.

The research is not intended to support a significant change in the advertising for the product.

The research does not involve a route of administration or dosage level or use in a patient population or other factor that significantly increases the risks (or decreases the acceptability of the risks) associated with the use of the drug product.

The research is conducted in compliance with the marketing limitations described in 21 CFR §312.7.

Drug insert is available and attached to the IRB protocol.

## Procedures Involved

**We anticipate that the procedures listed below will take about 30 to 40 minutes per patient. Each patient will have a complete ophthalmologic exam. Except as noted, the procedures below are not considered standard of care and are being conducted for the study alone.**

- A. Part 1: Pre-treatment data collection
  - External photographs, MRD1, MRD2, palpebral fissure height, tear meniscus height, Schirmer I test with anesthesia and ocular staining with fluorescein will be recorded.
- B. Part 2: Botulinum toxin or Placebo topical application
  - Subjects will be randomized to receive either 15 units of botulinum toxin A (BOTOX), incobotulinum toxin A (XEOMIN), prabotulinum toxin A (JEUVEA), the equivalent of 45 units of abobotulinum toxin A (DYSPORT) or balanced saline placebo in one eye after 10 patients are included for the interim analysis with BT eye drops topically on the surface of the eye
  - Then based on the randomization results, the examiner will apply botulinum eye drops or saline to the one of the subject's eyes.
- C. Part 3: Post-treatment data collection
  - Subjects will come back in 3 days, 1 week, 2 weeks, 1 & 3 months after they receive the treatment or control.
  - At each visit, subjects will have the measurements above again.
- D. Part 4: Data analysis
  - Data will be recorded and stored in a secure Microsoft Office Excel (Microsoft Corporation, Redmond, WA, U.S.A.) spreadsheet. Data will be graphically analyzed and represented with Adobe Photoshop (Adobe, Inc., San Jose, CA, U.S.A.).
  - Data assessed will involve assessing pre- and post-treatment MRD1 and MRD2, investigator-assessed measurements of ocular surface and tearing.
  - User performing analysis will be blinded to which eye received study drug.

Follow-up outside of the patient's next routine clinic visit will be needed for 3 days, 1 week, 2 weeks and 1 & 3 months. Patients who do have symptoms concerning any post-procedural complications will be instructed to notify study staff immediately. A phone number will be provided.

Outcomes Measures:

Primary outcome:

Outcome Measure Title: Change in palpebral fissure height

Outcome Measure Description: Palpebral fissure height will be calculated from the sum of marginal reflex distance 1 and 2 measured by the researcher.

Outcome Measure Timeframe: Baseline, day 3, 7, 14, 30 & day 90.

Secondary outcomes:

Outcome Measure Title: Change in eye ocular surface and tearing

Outcome Measure Description: Scoring of ocular surface and tearing will be done by fluorescein staining with a slit lamp and Schirmer I test with anesthesia.

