## 5) Procedures Involved\*

*Patients coming to the oculoplastic clinic who qualify for the study based on inclusion and exclusion criteria (With upper lid retraction or asymmetry>1mm) will have the study explained to them by a research study member and they can ask questions. They will receive information on risks and benefits to research participation. For interim analysis of futility, we will do the study with BT eye drops on first 10 patients and then evaluate the results to see if there are any significant effects. If clinically significant effects are seen, then 34 patients totally (17 in BT vs 17 in saline) are included. After a written consent is obtained, External Photographs will be taken by a standard camera in standardized room light. Eyelid measurements will be done including MRD1, MRD2, PF height with the eyes in the primary position. Tear meniscus height, Schirmer I test with anesthesia and ocular staining with fluorescein will be evaluated for all patients recruited before and after eye drops are installed by the PI or resident in the clinic in the eye with greater palpebral fissure height (one eye). In each visit all these data will be obtained again. The subjects will be allocated to the treatment based on the randomization sheet provided by the biostatics department that is handed to [name], Surgical Coordinator on the 4th who will inform the PI of the patient's number. After the PI sees the patient, she will inform the resident in the clinic. The resident or the fellow in the clinic will be asked to provide the PI with the eye drop (botulinum toxin A or saline in 1 cc syringes without needles) while not informing of the contents. The research team([name], [name], [name], [name]), also blinded to the study will gather the data and take the necessary photos (double Blinded).*

*Potential toxicity or life-threatening toxicity with topical botulinum toxin is unlikely.*

*Pressure on the lacrimal sac by the patients for 2 minutes will be done to minimize systemic absorption.*

*Patients will be provided a phone number to call if any complications occur.*

*BOTOX®, JEUVEAU, XEOMIN, and DYSPORT are Crystalline preparations of BT type A, FDA approved drugs for many indications including periocular wrinkles. Saline eye drops will be also used as placebo.*

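### For the randomised patients, the written steps on who prepares, instils and measures do not consistently deliver the stated double blind

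*Combined protocol and SAP*

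**What the plan says.** Section 5 (Procedures Involved) sets out the masking. The surgical coordinator receives the randomisation sheet, "who will inform the PI of the patient's number". Next, "After the PI sees the patient, she will inform the resident in the clinic". Then "The resident or the fellow in the clinic will be asked to provide the PI with the eye drop", in a needleless syringe, "while not informing of the contents". The research team is "also blinded to the study will gather the data and take the necessary photos (double Blinded"). Earlier in the same section, however, "eye drops are installed by the PI or resident in the clinic". Section 5 ends by saying that, if a side effect makes unblinding medically necessary, the PI learns the allocation by contacting a named person.

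The second, unnumbered Procedures Involved section describes the same step differently. Its Part 2 reads "Then based on the randomization results, the examiner will apply botulinum eye drops or saline". Under its outcome measures, "Palpebral fissure height will be calculated from the sum of marginal reflex distance 1 and 2 measured by the researcher". Part 4 of that section masks the person doing the analysis to which eye was treated and does not mention the treatment arm.

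**The concern.** The two accounts do not assign the roles in the same way. In section 5, the supplier of the syringe knows the arm and the PI who receives it does not. Yet the same section allows a resident to instil, and a resident may be the supplier. In Part 2, an examiner acts on the randomisation result. The word suggests someone who also examines the patient.

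This matters because the outcomes depend on human judgement. The primary outcome is the sum of two lid distances measured by a person, and the ocular surface is scored at the slit lamp. The hypothesis in section 2 is directional: fissure height is expected to fall. An assessor who knows the arm could shift readings that way without intending to. Measurements taken unmasked cannot be masked afterwards.

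The point concerns the randomised patients only. The first 10 patients all receive toxin, so they have no allocation to conceal.

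**Working it through.** **Step 1. Roles set side by side**

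| Task | Section 5 | Second Procedures Involved section |
|---|---|---|
| Supply the syringe | Resident or fellow | Not stated |
| Know the contents | Supplier, by implication: there is an instruction not to disclose | Examiner, if Part 2 is read literally |
| Instil the drop | PI or resident | Examiner |
| Measure lid distances | Blinded research team gathers the data | The researcher, not further defined |

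Three things follow.

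1. *Supply and instillation.* A resident may supply and a resident may instil. Nothing says that these must be different people.
2. *Instillation and allocation.* Section 5 has the PI receive a syringe of undisclosed content. Part 2 has the examiner act on the randomisation result. Read literally, these conflict.
3. *Measurement.* Section 5 assigns data gathering to a blinded team. The outcome definition names a researcher without saying that this person belongs to that team.

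**Step 2. What must happen for bias to arise**

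Knowing the arm while instilling does not change a lid measurement. Bias needs one further event: the person who knows the contents also measures, or tells someone who measures. The text does not state that either occurs. It instructs the supplier not to disclose and says the data gatherers are blinded, but it has no explicit rule that keeps the supplier or instiller from examining the patient.

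**Step 3. Illustration of size**

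The plan has no figure of its own to reproduce here. From the documents: 17 patients per group and alpha 0.05 (Number of Subjects). The documents give neither an SD nor an assessor bias, so the bias *b* is assumed and expressed in SDs of the change in fissure height.

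The calculation is the rejection rate of a two-sided two-sample t-test with no true effect and a between-arm shift of *b*:

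- degrees of freedom = 2 × 17 − 2 = 32
- non-centrality = b × √(17/2) = 2.915 × b
- rejection rate = P(|T| > t at 0.975 on 32 df), with T non-central t

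| Assumed bias *b* (SD) | Non-centrality | False-positive rate |
|---|---|---|
| 0 | 0 | 5.0% |
| 0.1 | 0.29 | 5.9% |
| 0.2 | 0.58 | 8.7% |
| 0.25 | 0.73 | 10.9% |
| 0.3 | 0.87 | 13.6% |
| 0.5 | 1.46 | 29.3% |

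Here *b* is the average difference between the arms. If only half of the readings were affected, a shift of 0.5 SD would enter as about 0.5 × 0.5 = 0.25 SD.

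The Data Analysis section names a paired t-test. The two-sample test is used here because it compares the randomised arms directly, so the table does not describe the operating characteristics of the planned test.

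**The case against.** The strongest reply is that section 5 already contains the safeguards that matter: the PI is not told the contents, and a blinded team gathers the data and takes the photographs. Someone who knows the contents is not blinded and so, by implication, is not on that team. This stands. It limits the point to an inconsistency and a missing explicit rule.

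Two alternative readings are also fair. Acting on the randomisation results may be loose wording for giving the allocated syringe. The clause allowing the PI or a resident to instil covers all recruited patients, so it may have the first 10 in mind. Neither reading is stated, and the literal text points the other way.

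A reader might go further in three ways that the documents do not support:

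- *That residents who know the arm will measure.* Section 10 credits residents with experience of slit-lamp work and data collection, but it gives them no measuring task in this trial. The team members' names are removed from the public text, so it cannot be seen whether a resident is among them.
- *That passing the patient's number through the PI breaks the blind.* The pronoun in that sentence could mean the PI or the coordinator. What is passed on is a patient number, and the unblinding provision implies that the PI does not otherwise know the arm. A supplier who holds the key is no defect, since that role is meant to be unblinded. It is enough that the number does not reveal the arm.
- *That the false-positive rates predict what this trial will do.* They follow from assumed biases and show only how sensitive a trial of this size would be.

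**Conclusion.** The point holds as a limited one. For the randomised patients, the protocol states a double blind but describes preparation, instillation and measurement inconsistently. Followed literally, its steps would let a person who knows the arm instil the drop, and they do not expressly stop that person from examining the patient. The documents do not show that the blind will fail.

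The size of any bias cannot be derived from the documents. Under the stated assumptions (no true effect, 17 per arm, two-sided two-sample t-test), the false-positive rate barely moves from its nominal level at 0.1 SD and reaches nearly six times that level at 0.5 SD (29.3 / 5 = 5.9). The case for changing the text rests on the contradiction between the two sections, on an outcome measured by a person, and on the low cost of the correction.

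**What to change.** Before randomisation starts, reconcile section 5 with the second Procedures Involved section for the randomised part:

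1. The resident or fellow who prepares a patient's syringe does not instil, photograph, examine or measure that patient at any visit.
2. The masked PI instils from an unlabelled syringe. This replaces the Part 2 wording in which an examiner acts on the randomisation result, and removes the resident as a possible instiller for these patients.
3. The researcher who measures MRD1 and MRD2 is defined as a member of the blinded team in section 5.
4. One sentence confirms that the patient number does not reveal the arm. The route by which the number is passed on can stay as it is.

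Masked reading of the photographs already planned would be a useful further protection, but the fix does not depend on it.

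The cost is protocol wording and a clinic rota rule, using roles that section 5 already names. The preparer cannot help with that patient's visits, and the PI has to be available to instil. The documents do not describe clinic staffing, so the site should check that both are workable.

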#### Adverse Events and Serious Adverse Events

Treatment-emergent adverse events, defined as any event, not present prior to the initiation of the drug treatment or any event already present that worsens in either intensity or frequency following exposure to the drug treatment, will be monitored and reported throughout the study. Treatment emergent adverse scale will be graded as the following:

- Mild: Transient or mild discomfort (<48 hours) to the subject; no medical intervention/therapy required.

- Moderate: Mild to moderate limitation in activity of the subject; no or minimal medical intervention/therapy required.

- Severe: Marked limitation in activity of the subject, some assistance usually required; medical intervention/therapy required including possible hospitalization.

Serious adverse events are defined as those which result in death, hospitalization, persistent or significant incapacity or substantial disruption of the ability to conduct normal life functions (aka disability), or congenital anomaly / birth defect.

Previously reported treatment-emergent adverse effects are described further in the risks section below.

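### Adverse events are to be monitored throughout, but no visit is required to ask about symptoms, and withdrawn subjects' data are shredded, so the safety record may be incomplete

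*Combined protocol and SAP*

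**What the plan says.** The section on Adverse Events and Serious Adverse Events defines a treatment-emergent event as one that is new after treatment, or one already present that becomes more intense or more frequent. It says such events "will be monitored and reported throughout the study". The Mild grade is "Transient or mild discomfort (<48 hours) to the subject", with no intervention needed. Moderate and Severe turn on limitation of activity and need for treatment. The section names no question, form or visit at which events are elicited.

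Visit content is described twice. Part 3 of Procedures Involved says "At each visit, subjects will have the measurements above again". The measurements meant are those of Part 1: photographs, MRD1, MRD2, fissure height, tear meniscus height, Schirmer I and fluorescein staining. Section 5 gives a similar list and says "In each visit all these data will be obtained again". The assessment times are "Baseline, day 3, 7, 14, 30 & day 90".

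Symptoms reach the study by patient contact. Section 5 says "Patients will be provided a phone number to call if any complications occur". Procedures Involved tells patients with symptoms that suggest a complication to notify staff at once. Section 6, Risks to Subjects, tells them to call about vision change, redness or pain.

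Under Withdrawal of Subjects, those withdrawn can include subjects with an adverse effect that requires stopping the medication. The data of any withdrawn subject are left out of the analysis and shredded.

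**The concern.** The grading scale needs information that the written visits do not collect. A photograph, a lid measurement or a Schirmer strip does not show a headache, how long it lasted, or whether it limited activity. If nobody asks, such an event enters the record only when the patient raises it, and enquiry may vary between examiners and visits.

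This matters because the Background says there have been no studies of a toxin drop of this kind, and section 6 says no topical ophthalmic solution has been evaluated. The event listing from this trial would be early safety information for the route, including that from the first 10 patients, all of whom receive toxin. The shredding rule could remove the very records that are most informative for safety.

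What is at stake is the completeness and timing of the safety record. The primary endpoint, palpebral fissure height, is measured at every visit and is not affected by how symptoms are elicited.

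**Working it through.** The plan gives no figure on this point, so the main check sets its statements side by side.

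1. **What must be known to apply the scale.** Discomfort, duration under or over 48 hours, limitation of activity, need for treatment, and worsening against a starting point.
2. **What the visits are written to record.** Photographs, lid position, tear measures and staining. These would show ptosis, a turned lid margin or corneal staining. They would not show headache, malaise, double vision or light sensitivity, all of which the protocol names as effects of injected toxin (Background; section 6).
3. **Other ways an event could reach the record.** Three instructions, each started by the patient (section 5; Procedures Involved; section 6). There is also a statement that "Each patient will have a complete ophthalmologic exam". That examination is not assigned to the follow-up visits and is not described as a symptom enquiry.
4. **What is planned for the data.** Part 4 of Procedures Involved lists lid, ocular surface and tearing measures. Data Analysis names fissure height, ocular surface and tearing. Neither mentions adverse events.
5. **What survives withdrawal.** The shredding sentence has no exception for adverse event records. Unanticipated problems or complications go to the IRB under section 6, so those reports should survive. Ordinary graded events have no such protection.

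So the commitment to monitor is stated, and the method of eliciting symptoms is not.

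**Illustration of scale, on assumed rates.** Let p be the true proportion of patients with a given symptom and s the share of those patients whose symptom is recorded. With n patients independent of each other, the chance of recording at least one case is 1 − (1 − p·s)^n. For n = 17 (the planned toxin arm):

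| Assumed p | s = 1 | s = 0.7 | s = 0.5 | s = 0.3 |
|---|---|---|---|---|
| 5% | 0.58 | 0.45 | 0.35 | 0.23 |
| 10% | 0.83 | 0.71 | 0.58 | 0.40 |
| 20% | 0.98 | 0.92 | 0.83 | 0.65 |

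For example, at p = 10% and s = 0.5, 1 − 0.95^17 = 0.58, against 1 − 0.90^17 = 0.83 at s = 1. For the first 10 patients at p = 10%, the values are 0.65 (s = 1) and 0.40 (s = 0.5).

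Neither p nor s is in the documents, and s = 1 is a ceiling that no question fully reaches. The table shows only that, with so few patients, incomplete recording can decide whether an uncommon symptom appears at all.

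**The case against.** The strongest reply is that the plan is silent on method, which does not mean it excludes asking. The adverse event section commits to monitoring throughout, and its definition and grades are hard to apply without talking to the patient. Part 3 describes outcome data, while adverse events have their own section. A reader might infer that symptoms will be recorded only if patients volunteer them. The documents do not support that as a statement about practice. What stands is narrower: no enquiry is required, so none can be counted on.

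The plan also softens the risk. Section 5 says "Potential toxicity or life-threatening toxicity with topical botulinum toxin is unlikely", the risks are explained to patients, they are told to report complications, and there are five follow-up visits within three months. Safety is neither an aim nor a listed outcome. All this stands and keeps the point modest. It does not fill the gap, because the plan itself promises to monitor and report these events.

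Two ways of making the point look larger should be resisted:

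- A reader might set the 48-hour limit of the Mild grade against the intervals between visits (3, 4, 7, 16 and 60 days) and calculate a share of events missed. That share depends on when symptoms begin, which the documents do not give. Overlap with a visit is also not the issue, since a question at a visit works by recall.
- A reader might count every effect named in the protocol that no measurement shows. Such a count mixes periocular effects with those that section 6 ties to neck or other non-periocular injections, so it does not describe the risk of a drop.

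Finally, the shredding rule would be a defect even with active questioning. It belongs here only because it affects the same record.

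**Conclusion.** The point holds in a limited form. The written procedures do not say how symptoms are elicited, and the withdrawal rule makes no exception for adverse event records. The safety record for a previously unstudied route may therefore be incomplete, and notice of a symptom may come late.

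The size is modest. The documents support no rate of missed events, and none is claimed. A reader might infer bias in the primary comparison. That does not follow: fissure height is measured regardless, no between-arm test of adverse events is planned, and under-reporting would be expected in both blinded arms.

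The conclusion assumes that the two descriptions of visit content are complete as written, and that the shredding sentence covers adverse event records, which it does not exempt. Consent pages are not available, so what patients are told there is not judged.

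**What to change.** 1. **Ask at every visit.** At baseline, before the drop, record current symptoms, because worsening needs a starting point. At each of the five follow-up visits, ask every patient one standard open question about new or worse symptoms since the last visit. Include the first 10 toxin-treated patients. Ask after the lid measurements, so that the answer does not cue the blinded examiner. Brief prompts are optional: double vision, light sensitivity, weakness, and trouble swallowing, speaking or breathing. Record onset and duration, grade on the existing scale, and list events by arm with the first 10 shown separately.
2. **Keep the records.** Add a sentence to Withdrawal of Subjects so that adverse event records collected before withdrawal are kept and reported.

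The statement in section 6 about discontinuing the study for negative effects should stay as it is. It is a participant safeguard, and this point gives no reason to narrow it.

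**Cost.** Six short forms per patient: 34 × 6 = 204, or 44 × 6 = 264 if the first 10 are additional to the 34, which the plan leaves unclear. At an assumed 2 to 5 minutes each, that is 204 × 2 / 60 = 6.8 hours to 264 × 5 / 60 = 22 hours over the whole trial. No new visit or test is needed. The downside is that more minor background events will be recorded in both arms.

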## **Number of Subjects**

10 Patient are recruited for interim analysis of futility. If significant, then 17 patients in each group (34 total) based on power calculations for alpha of 0.05 and power of 80% per the biostatistics department.

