### **Data Analysis**

Statistical analysis will be performed by the Oculoplastic Research Laboratory research fellow. A paired t-test will be used to analyze the difference in palpebral fissure height, ocular surface and tearing. 34 subjects will be required to perform perimetric statistics.

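### The plan names only a paired t-test and makes no use of baseline palpebral fissure height; adjusting for it would usually sharpen the 17 v 17 comparison at almost no cost

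*Combined protocol and SAP*

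**What the plan says.** The outcomes list under Procedures Involved gives the primary outcome as "Outcome Measure Title: Change in palpebral fissure height". It defines the measure thus: "Palpebral fissure height will be calculated from the sum of marginal reflex distance 1 and 2 measured by the researcher". The schedule is "Outcome Measure Timeframe: Baseline, day 3, 7, 14, 30 & day 90", with no visit singled out as primary. Part 1 of the same section has the baseline values collected before treatment: "External photographs, MRD1, MRD2, palpebral fissure height, tear meniscus height, Schirmer I test with anesthesia and ocular staining with fluorescein will be recorded".

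The analysis is one sentence under Data Analysis: "A paired t-test will be used to analyze the difference in palpebral fissure height, ocular surface and tearing". No covariate, ANCOVA, repeated-measures model or between-arm test is named there or anywhere else.

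The design is nonetheless a two-arm comparison. Section 5 says "then 34 patients totally (17 in BT vs 17 in saline) are included", and Number of Subjects says "then 17 patients in each group (34 total) based on power calculations for alpha of 0.05 and power of 80% per the biostatistics department". Section 5 also has the drop placed "in the eye with greater palpebral fissure height (one eye".

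**The concern.** A paired t-test of before versus after gives a within-patient change. It does not estimate the BT-minus-saline difference and cannot take a covariate. The most natural minimal repair is a two-sample t-test on raw change. That would supply the missing comparison but still leave the baseline measurement unused.

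With 17 per arm, precision is scarce. A raw change score fixes the baseline coefficient at 1, whereas the data will generally support a smaller one. The result is usually a wider confidence interval than the same patients could give. It also leaves an estimate that moves with whatever baseline difference chance puts between the arms.

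**Working it through.** **1. The plan's own figure.** The 17 per group cannot be reproduced: no effect size, SD, sidedness or test is given for the power calculation. It can only be back-solved, assuming a two-sided 5% test.

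- Normal approximation: d = (1.960 + 0.842) × sqrt(2/17) = 0.961.
- Two-sample t-test, 32 df: 80% power at d = 0.991. At d = 1.0, 17 per arm gives 80.7%.

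So 17 per arm fits an effect of about 1 SD of whatever quantity was compared. Below, the starting point is a two-sample t-test on raw change with exactly 80% power (d = 0.991 SD of change).

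**2. Variance with and without adjustment.** Assume equal SD σ at baseline and follow-up, and correlation rho between them. Rho is an assumption shown as a range.

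- Per-patient variance of change: 2(1 − rho)σ².
- Per-patient residual variance after ANCOVA: (1 − rho²)σ².
- Ratio: (1 + rho)/2.
- Cost of estimating the slope with N = 34: factor 1 + 1/(34 − 4) = 1.033.

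The adjusted standardised effect is 0.991/sqrt(ratio with cost), tested on 31 df:

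| rho | (1 + rho)/2 | with small-sample cost | power, raw change | power, adjusted |
|---|---|---|---|---|
| 0.3 | 0.65 | 0.67 | 80% | 92.7% |
| 0.5 | 0.75 | 0.78 | 80% | 88.9% |
| 0.7 | 0.85 | 0.88 | 80% | 84.8% |
| 0.8 | 0.90 | 0.93 | 80% | 82.7% |
| 0.9 | 0.95 | 0.98 | 80% | 80.6% |
| 0.95 | 0.975 | 1.01 | 80% | 79.6% |

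Break-even is where (1 + rho)/2 × 1.033 = 1, so rho = 2/1.033 − 1, or about 0.94. Simulation with 20,000 trials per setting gave variance ratios of 0.67, 0.77, 0.88, 0.99 and 1.01 at rho 0.3, 0.5, 0.7, 0.9 and 0.95. The adjusted powers were 92.7%, 88.9%, 84.7%, 80.3% and 79.7%.

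The interval width scales with the square root of the ratio. It is about 18%, 12%, 6%, 4% and 1% narrower at rho 0.3, 0.5, 0.7, 0.8 and 0.9.

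**3. Chance baseline imbalance.** With 17 v 17 fully randomised, the baseline mean difference D has standard error sqrt(2/17) = 0.343 SD. The chance that it exceeds 0.5 SD in either direction is 2 × P(Z > 0.5/0.343) = 2 × P(Z > 1.458), about 14%. Given D, the raw-change difference carries an error of −(1 − rho)D. At D = 0.5 SD that is −0.25 SD at rho 0.5, −0.15 at 0.7 and −0.05 at 0.9.

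This is not a second cost on top of step 2. In units of σ² per patient, 2(1 − rho) = (1 − rho²) + (1 − rho)². The last term is the imbalance error. As a share of the total it is (1 − rho)/2, exactly what adjustment removes before the small-sample cost.

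**The case against.** Several points against the concern stand, and they limit what can be claimed.

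- **The outcome label excludes nothing.** ANCOVA can be run on change and gives the same arm effect as ANCOVA on follow-up height. The evidence lies in Data Analysis, where the only test named cannot be adjusted.
- **No between-arm test is in the plan.** The absence of a BT-versus-saline test is the more basic defect, and the precision loss is conditional on how it is repaired. But repairing it with an unadjusted test on change would leave the present point open, while one sentence can settle both.
- **Rho may be high.** The same eye is measured repeatedly, and patients with variable lid position are excluded. At 0.9 the gain is under one power point, and above about 0.94 there is none.
- **Change need not depend strongly on baseline.** A reader might infer strong dependence because the wider eye is chosen. No figure in the documents supports that. Under the equal-SD model the correlation of change with baseline is −sqrt((1 − rho)/2): −0.39 at rho 0.7, −0.32 at 0.8 and −0.22 at 0.9.
- **Eye selection does not bias the comparison.** A reader might infer that choosing the wider eye makes a raw-change result wrong through regression to the mean. The rule applies to both randomised arms alike, so the expected fall-back cancels in the arm difference.

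**Conclusion.** The point holds as a nearly free improvement. Baseline height is collected, the analysis makes no use of it, and the one test named could not use it. A between-arm analysis of raw change would be valid under randomisation but usually less precise than an adjusted one. The gain is roughly 5 to 13 power points at rho 0.7 to 0.3, about 3 at 0.8 and under 1 at 0.9. It is nil near 0.94, with a loss of under half a point at 0.95.

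A reader might infer that the unadjusted result would be biased, or that imbalance is a harm additional to lost precision. Neither follows: the −(1 − rho)D error averages to zero over randomisations and is already in the change-score variance.

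The figures assume equal SDs, 17 randomised and analysed per arm, a two-sided 5% test and 80% power on raw change. The protocol does not say whether the first 10 patients, all given BT, count among the 34. If they do, baseline differences are not due to chance alone, and adjustment does not turn those patients into part of a randomised comparison. Withdrawn patients are dropped from the analysis, so 17 per arm may also not be reached.

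**What to change.** In Data Analysis, replace the paired t-test for the primary outcome with the following:

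- The estimate is the BT-minus-saline difference in palpebral fissure height of the study eye, among randomised patients.
- It comes from ANCOVA with arm and the patient's own baseline palpebral fissure height, at a named primary visit. If all visits are analysed together, use a repeated-measures model with baseline as a covariate.
- The unadjusted difference is reported as a sensitivity result.

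Treat the Schirmer test the same way, with its own baseline value. For staining, adjust for baseline with a method suited to its scoring scale. The protocol does not describe that scale, so a linear model should not be assumed to fit.

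The cost is one degree of freedom and a sentence or two of text, with no new data, visits or patients. Fixing the model in advance also prevents a choice between adjusted and unadjusted results after the data are seen.
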